### **Subsection 2.4 - Phase II Recruitment & Screening**

Women will be recruited from Prototypes, a HealthRIGHT 360 RDTS. The RDTS staff will assist the PI and GSR in providing approximately two informational meetings (advertised through UCLA IRB-approved flyers and verbally by staff) for interested women where they will be informed about the opportunity. Recruitment flyers will also be posted around the RDTS. GSRs and RAs will help recruit women and conduct the initial screening in a private room or in an area onsite where the interview can not be overheard by others after completing the Consent to Screen Script. Progress will be monitored closely by [name] the Lab Management team.

There will be eight cohorts in total, each with two intervention groups of 12-14 WEH (see Table 2). Each cohort will receive the same intervention (e.g., in Cohort 1 there will be two groups of MSC, in Cohort 2 there will be two groups of TAU). The cohorts will be divided into two smaller groups of 12-14 WEH (24-26 per cohort) rather than one large group of 24-26 WEH. Recruitment and the intervention for each cohort will take approximately 6-8 weeks to complete.

[name] and/or lead GSR(s) will explain the study during an initial meeting with potential participants and answer any questions. Then women will be screened for eligibility. Prior to obtaining any data, the women will provide a "consent to screen". This is because we need to obtain data from the women to determine if they are eligible, but they are not officially enrolled as human subjects. By providing their "consent to screen", we are obtaining verbal consent/permission to ask them questions. Their data will not be used by the research team if they are not eligible.

A member of the research team will read the consent to screen script exactly as written on REDCap. Potential participants are free to stop at any time – remind them that all procedures are completely voluntary. [name] and/or someone from the Lab Management team (e.g., GSR) will always be onsite to help answer questions.

The RA or GSR will then administer the eligibility screener to participants via iPad. The screener will first assess age, prior homelessness, and cognitive impairment. Cognitive impairment will be determined by a score greater than 9 on the Short Blessed Test. The screener then screens for PTSD using the PTSD Checklist for DSM-5 (PCL-5) for the worst event in their life. We will assess PTSD to their most recent event (in the past year) during the baseline and follow-up assessments. The standard PCL-5 initially starts with the identification of the presence of exposure to a DSM-5 traumatic event and then assesses whether it involved actual or threatened death, serious injury or sexual violence. The RA may need to prompt the potential participant with examples to keep them on track and to ensure that the participant is responding to an actual DSM-5 traumatic event. The next 20 items on the PCL-5 assess all four B-E PTSD criterion (re-experiencing, avoidance, negative thoughts or cognitions, hyperarousal), assessed on a Likert-type scale 0 "not at all", 1 "a little bit", 2 "moderately", 3 "quite a bit", 4 "extremely". Subthreshold PTSD will be defined as endorsing "moderately" or more to at least 2 B-E criteria; probable-PTSD will be measured by meeting criteria A-G for PTSD.

**Data collection method:** All data will be collected via iPads using REDCap and will be immediately transferred to UCLA's secure server.

All participants who complete the screener will receive \$5. It is very important to compensate all individuals who participate in the screening, even if they are not eligible!!!

Subsection 2.5 - Phase II Eligibility Criteria

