### **Subsection 1B.2 MSC Basics**

MSC is a mind-body integrative health intervention that utilizes meditations, other contemplative practices, home practices, and experiential exercises (including group discussions) to increase SC. MSC can be done in groups of 10-25. The full program typically consists of eight sessions, approximately 2.5 hours long, and a 4-hour (half-

day) silent retreat. There are a total of 25 practices in MSC (including three core meditations, four other meditations, and 18 informal practices for daily life); all incorporate loving-kindness (e.g., self-compassion). An official MSC adaptation, the MSC short course consists of six sessions and has been increasingly used in healthcare settings.  Our prior work with WEH found that the majority of WEH completed 7/9 available sessions (6 sessions or more were considered treatment completion), with most WEH citing early discharge from RDTS as the reason for lower dose of sessions. To increase feasibility of MSC for use in RDTSs, we will aim to adapt MSC to 7 sessions (6 weekly sessions in alignment with the MSC short course plus the half day retreat included in the full course to facilitate skill consolidation). Sessions will be conducted in a group-based format: prior research found group-based formats equivalent to individual-level interventions for PTSD/SUD.

**Table 1.** Progression of the adapted 6-week MSC intervention

Table 1. Overview of Key MSC Practice by Session								
Session	Topics	Key Practices for PTSD/SUD						
Session 1 What is MSC?	Why Am I Here? How to Approach MSC Guiding Principles 3 components of SC Misgivings	"How do I treat a friend"? Physiology of SC and Criticism SC Break Informal Practice: SC Bracelets						
Session 2 Practicing SC	"Resistance & backdraft" How We Cause Ourselves Unnecessary Suffering Development of Safety & Trust Inner Ally	Affectionate Breathing Practicing Loving Kindness Soles of the Feet Mindfulness & SC in Daily life Here and Now Stone						
Session 3 Discovering Your Compassionate Voice	Self-Criticism & Safety Core Values Compassionate Conversations with Self	Meeting the Inner Critic Finding Phrases Compassionate Letter to Ourselves						
Session 4 SC & Resilience	Applying SC to Difficult Emotions Hidden Values in Suffering Emotion of Shame Described & Demystified	Core Values Exercise Living with a Vow Silver Linings						

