#### **SECTION 2. INTERVENTION DELIVERY**

#### **Subsection 2.1 - Phase II Overview**

In Phase II, we will assess the benefit of MSC to produce improvements in primary (PTSD, SUD) and secondary outcomes (depression, anxiety, hopelessness, loneliness) compared to Treatment as Usual (TAU) and to explore mechanisms of symptom change over time. We will implement an open-label cluster randomized clinical trial of an adapted MSC course for PTSD/SUD with WEH (N=202), randomized to MSC (n=101) or TAU (n=101). Women will be recruited from Prototypes, a HealthRIGHT 360 RDTS. Inclusion criteria will be: 1) woman age 18 and over; 2) probable PTSD as judged by the PCL-5 (score of 31 or higher, indicated as having optimal signal detection); 3) no cognitive impairment according to a score of < 10 on the Short-Blessed Test; 4) experienced homelessness in the past 6 months or prior to incarceration ("spent night in public or private shelter or on the street"); and 5) able to speak and understand English. We will recruit 8 cohorts of 24-26 WEH and each cohort will be divided into 2 groups. Cohorts of participants will be randomized to an adapted MSC course or TAU prior to enrollment of the first participant and randomization will occur at the level of the cohort rather than the participant. This is to minimized contamination in cohorts as women live together at the RDTS but cycle out after ~3 months. Women receiving MSC or TAU will complete psychosocial questionnaires, demographics, and a Locator Guide at baseline. Women receiving MSC will participate in weekly MSC classes for 6 weeks, followed by a post-intervention follow-up and 4-month follow-up. Women receiving TAU will complete short psychological surveys each week for 6-weeks, followed by a 6-week post-baseline and 4-month follow-up.

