#### e. Intervention

i. Participants will participate in a seven session (six sessions + retreat) adapted MSC short course administered over a 6-week timeframe or TAU. WEH will be compensated \$10 per session.

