### g. 4-Month Follow-Up

i. Four months after baseline (approximately 2 months after post-assessment), primary and secondary outcomes will be re-assessed, in addition to key covariates and recent negative life events. Participants will be contacted using the Locator Guide and compensated \$30. These sessions will occur in person (at a private location convenient for the participant) or over Zoom as requested by participant.

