#### **Inclusion Criteria:**

- 1) Unhoused women or individual who identifies as a woman (N=202; 101 in each group)
  - a. Women over 18 years of age
  - b. Able to speak English
  - c. Experienced homelessness in the last 6 months: a homeless person is defined as anyone who spent the previous night in a public or private shelter, or on the street.
  - e. Likely subthreshold or threshold PTSD, as measured by the PCL-5.
  - f. No cognitive impairment according to a score of < 10 on the Short-Blessed Test

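### Time already spent in residence at enrolment is neither recorded nor adjusted for, although it sets how long a woman has been discharged when she reaches the 4-month visit

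*Combined protocol and SAP*

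**What the plan says.** Subsection 2.1 justifies cluster randomization by noting that "women live together at the RDTS but cycle out after ~3 months". Subsection 2.2 (e) describes a "seven session (six sessions + retreat) adapted MSC short course administered over a 6-week timeframe or TAU", and Subsection 2.4 adds the time needed to fill a cohort: "Recruitment and the intervention for each cohort will take approximately 6-8 weeks to complete". The final visit is tied to baseline, not to admission or discharge (Subsection 2.2, g): "Four months after baseline (approximately 2 months after post-assessment), primary and secondary outcomes will be re-assessed".

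Subsection 1B.2 reports that in the team's earlier work the majority completed 7 of 9 sessions, "with most WEH citing early discharge from RDTS as the reason for lower dose of sessions", and the course was then set at seven sessions.

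On entry, Subsection 2.4 says: "The screener will first assess age, prior homelessness, and cognitive impairment". The PCL-5 follows. The lists in Subsections 2.1 and 2.5 contain no rule on time since admission. The look-back in Subsection 2.5, "Experienced homelessness in the last 6 months", is longer than the stay and so does not limit it. The measures in Subsection 2.7 include no admission date, and Section 3 names no covariate for time in residence.

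**The concern.** Because the last visit is timed from baseline, a woman enrolled on admission and one enrolled near the end of her stay reach it after very different periods in the community. Section 3 quantifies substance use as time to first use, days of use and relapse status, all of which depend on time at risk. If opportunity to use differs between residence and the community (an assumption, since the documents give no figure), part of the spread in a primary outcome is fixed before treatment starts and appears in no model. That costs precision. With four cohorts per arm, average time in residence could also differ between arms by chance. Time in residence bears as well on how much of the course is delivered during the stay.

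**Working it through.** **Inputs.** Stay S of about 3 months (Subsection 2.1), taken as 90 days; this rounding is an assumption. Final visit at 4 months from baseline (Subsection 2.2, g), or 122 days. Course of 6 weeks (Subsection 2.2, e), or 42 days. Six weekly sessions with the retreat between Sessions 5 and 6 (Table 1) can also span only 5 × 7 = 35 days from first to last. Recruitment plus course takes 6 to 8 weeks (Subsection 2.4), so the lead from baseline to first session is about 0 to 2 weeks.

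**The plan's own interval.** The plan puts the final visit about 2 months after the post-assessment. From baseline to the last session is 42 to 56 days on a 42-day course, so the gap is 122 − 56 = 66 to 122 − 42 = 80 days, or 2.2 to 2.6 months. This agrees roughly with the plan.

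**Discharge to final visit.** Let e be the time already in residence at baseline. Discharge comes S − e after baseline, so the visit comes 4 − (S − e) months after discharge. With S = 3 this is 1 + e:

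- e = 0: 1.0 month
- e = 1.5: 2.5 months
- e = 3: 4.0 months

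In days it is 122 − (90 − e) = 32 + e, or 32 to 122, nearly a fourfold range (122/32 = 3.8). As a share of the 122 days since baseline, time in the community runs from 32/122 = 26% to 100%. The interval is 1.5 to 4 months for a 2.5-month stay and 0.5 to 4 months for a 3.5-month stay. The upper end requires baseline on the last day of the stay.

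**Share discharged before the last session.** This needs the distribution of e, which the documents do not give. If e is spread evenly over 90 days, the share is (lead + course span)/90:

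| Course span | No lead | 1-week lead | 2-week lead |
|---|---|---|---|
| 35 days | 35/90 = 39% | 42/90 = 47% | 49/90 = 54% |
| 42 days | 42/90 = 47% | 49/90 = 54% | 56/90 = 62% |

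If all women enrol in their first 30 days, each has at least 60 days left. The longest requirement is 56 days, so the share is 0%.

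**Could the analysis pick it up as written?** Section 3 adjusts for covariates that differ statistically between cohorts at baseline, and screens candidates for PTSD at p<.05, with the same approach for secondary outcomes. Neither step can act on a variable that no part of the plan says is collected. A random cohort effect allows for cohort-level variation in the standard error but does not remove an arm imbalance, and it leaves the spread within cohorts untouched.

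**The case against.** The protocol is aware of discharge. It shortened the course, assesses women who have left off site or by Zoom (Subsection 2.2, f), and has a detailed tracing plan. The covariate list for PTSD is introduced as examples, and the demographic items are not itemised, so the absence of an admission date is inferred. These points stand, but none of them records time in residence or commits the analysis to using it.

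A reader might infer that about half the MSC women will miss the end of the course, and that the effect and power are diluted accordingly. The documents do not support that:

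- The share runs from 0% to 62% on an entry pattern they do not give.
- They do not say that discharge ends attendance. Subsection 2.2 (d) says nearly all women move to sober living close to the site.
- Subsection 1B.2 speaks of "most WEH citing early discharge from RDTS as the reason for lower dose of sessions", which concerns leaving early, not enrolling late. Most women in that work still completed 7 of 9 sessions.
- A diluted-power figure would also need benefit proportional to sessions available, and would have to assume that the effect size of .3, drawn from earlier intervention studies, does not already reflect incomplete attendance.

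A reader might also infer bias between arms. Both arms share the site, eligibility rules, seven contacts over six weeks (Subsection 2.9) and visit times. Open-label assignment fixed before enrolment leaves room for a difference in time in residence, but nothing in the documents shows one.

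**Conclusion.** The point holds as a gap in measurement and adjustment. For a 3-month stay, the interval from discharge to the final visit can range from about 1 to 4 months for a reason settled at enrolment, and the plan neither records nor models it. The consequence is avoidable noise, chiefly in the substance-use outcomes, and possible chance imbalance across four cohorts per arm. The size of either depends on how time in residence varies within and between cohorts, which the documents do not show. The 39% to 62% range rests on even enrolment over 90 days and is illustrative only. This is a low-cost improvement; the plan is not shown to be biased or underpowered on this account.

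**What to change.** In Subsection 2.4, record the RDTS admission date at screening or baseline, and the planned discharge date for description. In Section 3, name days in residence at baseline as a covariate in every post-intervention and 4-month outcome model, fixed in advance and exempt from the p<.05 screening. It is determined before treatment, so adjusting for it is sound. Time since actual discharge arises after baseline and could be affected by treatment, so it should not replace it. Report the distribution of days in residence by arm and cohort.

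The cost is one or two dates from site records and one model degree of freedom, with no effect on recruitment. The dates should be taken at enrolment, because identifying data are destroyed at study end (Subsections 2.16 and 2.18) and the plan sets out no way to recover them later. Restricting entry by remaining stay, or giving priority to women with the longest stay ahead, is not recommended here: either would change the population studied.

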#### **Inclusion Criteria:**

- 1) Unhoused women or individual who identifies as a woman (N=202; 101 in each group)
  - a. Women over 18 years of age
  - b. Able to speak English
  - c. Experienced homelessness in the last 6 months: a homeless person is defined as anyone who spent the previous night in a public or private shelter, or on the street.
  - e. Likely subthreshold or threshold PTSD, as measured by the PCL-5.
  - f. No cognitive impairment according to a score of < 10 on the Short-Blessed Test

#### **Exclusion Criteria:**

The following will not be eligible for participating:

- 1) Persons who are:
  - a. Not able to speak English
  - b. Judged to be cognitively impaired, as indicated by score > 10 on the Short-Blessed Screener
  - c. Do not meet other inclusion criteria

#### **Subsection 2.6 - Phase II Intervention Program Description**

**General Description:** Among 202 eligible trauma-exposed WEH, assess the

impact of the MSC intervention at improving primary (PTSD, substance use) and secondary outcomes (depression, anxiety, suicidality) in WEH at a RDTS.

Data Collection Time points: Baseline, Post-Intervention follow-up, 4-month follow-up

**Total Duration: 4 months** 

### The following sections will outline the intervention process:

- Pre-intervention Assessments
- MSC Intervention
- Treatment as Usual
- Post-Assessment
- Dealing with Program Attrition
- Follow-up

#### Subsection 2.7 - Phase II Pre-Intervention Assessments

After Informed Consent, participants will complete a series of self-report measures. These measures will be administered by Research Staff at a private location at the site. Responses options to each question will be provided to the participant, organized in a clearly labeled binder. The Research Staff will display the response options for each measure, read the options out loud, and then record the response on the tablet. At the end of each measure, the RA will "lock" the measure. There will be a prompt if any items have been missed. Please check that there is no missing data. The participant may take a break at any time.

#### **Assessments**

#### Primary outcomes:

• PTSD PCL-5 (lifetime, past year)

PTSD symptoms will be measured using the PTSD Checklist for DSM-5 (PCL-5),  $^{1,2}$  which will be scored continuously and according to diagnostic criteria. The PCL-5 initially starts with the identification of the presence of exposure to a DSM-V traumatic event; assesses actual or threatened death, serious injury or sexual violence; and whether the person directly experienced it. Twenty additional items assess all four B-E criteria (re-experiencing, avoidance, negative thoughts or cognitions, hyperarousal), assessed on a Likert-type scale from 0 (not at all) to 4 (extremely). Treatment response will be defined as a  $\geq$  5-point reduction in symptoms and clinically meaningful improvement as  $\geq$  10-point reduction in symptoms. PTSD will be assessed for worse lifetime event and (if applicable) worst event in the past year.

Alcohol Use Disorders Identification Test (AUDIT)
 The AUDIT is part of the National Institute on Drug Abuse (NIDA)
 Clinical Trials Network (CTN) Common Data Elements for use in

clinical trials. The Audit is a 10-item alcohol screen that helps identify persons who are hazardous drinkers or who have active alcohol use disorders. It can be calculated as a sum score and will be analyzed as a continuous and categorical (yes/no used alcohol) outcome.

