#### SECTION 1A. RESEARCH STUDY OVERVIEW

#### **Subsection 1A.1 Overview & Introduction**

This three-year study will be a mixed-method, open-label cluster randomized clinical trial to test the benefit of the adapted mindful self-compassion intervention (MSC) at improving primary (PTSD, substance use) and secondary outcomes (depression, anxiety, helplessness, loneliness) among a sample of women experiencing homelessness (WEH) with PTSD/SUD residing in a residential drug treatment site (RDTS). An exploratory aim will be to elucidate mechanisms of treatment-response and maintenance or remission of symptoms.

Phase 1 of this three-year study was completed in December 2023. In Phase 1, a Community Advisory Board (CAB) was created, with women from the RDTS as well as site staff (including clinicians and substance use counselors). The CAB and the UCLA research team jointly created a semi-structured interview guide that was used with four focus groups (total N=27) of trauma-exposed WEH living at the RDTS. The participants completed acceptability and feasibility questionnaires and provided feedback on program design and administration. These suggestions were brought to the CAB and together the study design was finalized accordingly.

Phase II of this study will begin in Winter/Spring 2024. This will be a clinical trial comparing the MSC intervention to treatment as usual (TAU).

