### • Drug Abuse Screening Test-10 item (DAST)

The AUDIT is part of the NIDA CTN Common Data Elements for use in clinical trials. The DAST is a 10-item brief, self-report instrument for population screening, clinical case finding and treatment evaluation research. It can be used with adults and older youth. The DAST-10 yields a quantitative index of the degree of consequences related to drug abuse. The instrument takes approximately 5 minutes to administer and may be given in either a self-report or interview format. The DAST may be used in a variety of settings to provide a quick index of drug abuse problems. It will be evaluated continuously and as a categorical outcome (yes/no).

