### Assessments (see detailed description above)

### Primary outcomes:

- PTSD PCL-5 (lifetime, past year):
- Substance use AUDIT DAST

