# Section 3 – Data analytic plan

• *Power analysis*. Sample size was estimated using G\*Power and standard guidelines for testing mediation,  with α=.05, β=.80, and the standard deviation bound at ±1.91. Effect size estimates were derived from prior research on SC interventions for PTSD, which found a small-medium effect size (Cohen's d=0.2-0.5).  Particularly since the effect of MSC to reduce PTSD symptoms is emerging research, findings have been mixed regarding effect sizes for direct and indirect effects of SC interventions on PTSD, with some studies finding large effects of reduced PTSD due to SC interventions,  and others finding medium effect sizes.  (Of note, few randomized trials have been conducted).  To account for additional covariates, the clustering design,  and Type 1 error due to multiple tests, a small-medium effect size of .3 was conservatively estimated. Sample size appropriate for mediation was derived from a percentile bootstrap method, which simulations consistently show to be the most powerful test compared to similar methods (e.g., Sobel, bias-corrected bootstrap).  This yielded a final sample size of 162. Based on the team's prior research, we conservatively estimate 80% retention over time for a target enrollment of 202, for a total of 8 cohorts of 24-26 participants (divided equally into two groups per cohort). In the

team's prior work, 82% of those screened were eligible for participation: thus, we will aim to screen 246 WEH.

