- To evaluate reductions in PTSD symptoms, first, treatment response ( $\geq$  5-point reduction in symptoms) and clinically meaningful improvement (≥ 10-point reduction in symptoms) will be calculated for both immediate and 4-month follow-up. Potential covariates (e.g., demographic indicators; type, timing and amount of trauma exposure, including history of incarceration) will be screened for inclusion (included if p<.05). Change over time will be analyzed, using data from the three time points, using a mixed-effects repeated measures approach. This will also allow for a test of fixed (e.g., treatment group) and random (e.g., cohort) effects over time and conserves power by capitalizing on the longitudinal design. Reductions in PTSD will be examined using a modified Poisson distribution with robust variance, which tends to be less biased than a logit-based approach. Reductions in symptoms (measured continuously) will also be evaluated using a Gaussian distribution. Substance use will be evaluated using the TLFB, quantified as time to first use, days of use and relapse status (abstinent [did not use], lapse [used after study intervention but did not revert to regular use], or relapse [used substances for more than one third of days]). 34,35 Group x time contrasts will be tested. Identical analytic approaches will be used to examine secondary outcomes (suicidality, depression, and anxiety).
- To test for mediation effects, AGReMA (A Guideline for Reporting Mediation Analyses of Randomized Trials and Observational Studies) will be followed. A series of longitudinal structural equation models (SEM) will examine both direct and indirect effects by which change in mediators (emotion regulation, trauma-related guilt, trauma-related shame, moral injury and craving) are associated with change in PTSD, substance use, and secondary outcomes over time. Confidence intervals for indirect effects will be obtained through percentile bootstrap. SEM has the capacity to test for bidirectional

effects between PTSD symptoms and substance use. Model fit (e.g., Root Mean Square Error of Approximation) will be compared to find hypothesized paths that best fit the data.

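### Substance use is a primary outcome, but no measure, version or visit is named as deciding it, and the analysis section uses a different instrument from the assessment lists

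*Combined protocol and SAP*

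**What the plan says.** Subsection 1A.1 sets the aim of "improving primary (PTSD, substance use) and secondary outcomes". Subsection 2.6 repeats substance use as primary; Subsection 2.1 writes SUD in the same place.

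Under the primary outcomes in Subsection 2.7, the AUDIT, described as an alcohol screen, carries this instruction: "It can be calculated as a sum score and will be analyzed as a continuous and categorical (yes/no used alcohol) outcome". The DAST, described as an index of the consequences of drug abuse, carries a parallel one: "It will be evaluated continuously and as a categorical outcome (yes/no". No cut is given for the DAST yes/no version, and no recall period for either instrument. Subsection 2.10 lists the same pair at post-assessment: "Substance use AUDIT DAST".

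Section 3 names neither instrument. It says: "Substance use will be evaluated using the TLFB, quantified as time to first use, days of use and relapse status". The TLFB does not appear in the assessment lists of Subsections 2.7 or 2.10.

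The data collection points are "Baseline, Post-Intervention follow-up, 4-month follow-up", with neither follow-up marked as primary. On testing across time, Section 3 says only "Group x time contrasts will be tested". The power analysis is run "with α=.05, β=.80, and the standard deviation bound at ±1.91". It mentions Type 1 error from multiple tests once, as a reason for assuming an effect size of .3.

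**The concern.** One primary construct has four directed versions in Subsection 2.7 and three more quantities in Section 3, with no order among them. The lack of a ranking has two consequences.

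The first is the error rate. If each version is tested at .05 and any of them can support a statement that MSC improves substance use, the false-positive rate for that statement is well above .05. Choosing a smaller effect size changes the sample size; it does not control the error rate of any test.

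The second is meaning. Alcohol and drug results are different findings. A multiplicity correction alone would not say which version of each instrument is tested, or what is concluded about substance use if one class improves and the other does not. Nor can a reader tell whether the data behind the Section 3 analysis will be collected at all.

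**Working it through.** **Count of versions**
- AUDIT score and yes/no, DAST score and yes/no: 2 + 2 = 4 per visit (Subsection 2.7).
- Two follow-ups: 4 × 2 = 8.
- Adding the three TLFB quantities of Section 3: 4 + 3 = 7 versions, or 7 × 2 = 14 if each were tested at both visits.

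**Plan's own figures.** The plan gives α = .05 and no family-wise rate for substance use, so there is no stated error rate to reproduce. Its evaluable sample is 162, so 162/2 = 81 per arm at 1:1 allocation. The enrolment target agrees: 162/0.80 = 202.5, against 202.

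**If the tests were independent.** P(at least one false positive) = 1 − 0.95^k.
- k = 4: 0.1855
- k = 7: 0.3017
- k = 8: 0.3366
- k = 14: 0.5123

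**Allowing for correlation, four versions at one visit.** The documents give no use rates or correlations, so these are assumptions.
- Simulated trials: 81 per arm, no cohort effect, alcohol use 20–30%, drug use 30–50%, latent alcohol–drug correlation 0.3–0.7, a severity score among users, two-sided .05 tests. At least one of the four is significant in about 13–15% of null trials. A single any-use test stays at about 4–6%.
- Correlated normal statistics, 0.5–0.8 within an instrument and 0.2–0.5 between: about 14–17%.
- One common correlation of 0.3 to 0.8 among all four: 17.4% down to 11.4%.

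**Both visits.** Testing the four versions separately at each visit gives about 23–26% in the simulated trials and 24–29% with the correlated normal statistics above (0.5 between visits). Section 3 plans a mixed model over three time points with random cohort effects, so these figures show direction only.

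**How often versions disagree** (same set-up, single visit). When MSC helps in both classes, the share of trials with some but not all four versions significant is:
- alcohol 40% to 15%, drugs 60% to 30%: about 20–23%
- alcohol 30% to 25%, drugs 50% to 42%: about 27–30%
- alcohol 30% to 20%, drugs 50% to 30%: about 66–70%

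In the last of these, significant results in opposite directions occur in under 0.1% of trials. If substitution from drugs to alcohol is assumed, a significant drug benefit together with a significant alcohol harm occurs in:
- drugs 50% to 38%, alcohol 20% to 28%: about 4–8%
- drugs 50% to 30%, alcohol 20% to 25%: about 7–11%
- drugs 50% to 30%, alcohol 20% to 35%: about 42–54%

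**Price of two candidate remedies**
- Any-use composite, drugs 50% to 30% with alcohol at 30% in both arms: power is about 74% for drug yes/no and about 40–41% for any use.
- Holm across two scores: the first step uses .05/2 = .025. For a simple two-mean comparison, power ≈ Φ(d√(81/2) − z). At d = 0.44, 2.80 − 1.96 gives 80% and 2.80 − 2.24 gives 71%. At d = 0.3, 1.91 − 1.96 gives 48% and 1.91 − 2.24 gives 37%. This is the largest loss, because the second score regains .05 once the first is significant.

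**The case against.** The strongest reply is that Section 3 is the analysis plan and settles the matter: substance use is judged by the TLFB, and the AUDIT and DAST are descriptive. The text does not support that. Section 3 gives three TLFB quantities without ranking them, does not demote the AUDIT or DAST, and relies on an instrument that neither assessment list includes. Subsection 2.7 still says that both instruments will be analysed in two ways, as primary outcomes. What stands is that running the four AUDIT/DAST versions is only half of what the documents direct, so the role of the TLFB has to be part of the answer.

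A second reply is that the mixed model gives one result per outcome. Each version would still need its own model, and no deciding contrast is named.

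Several stronger readings are tempting and go too far.
- *The versions will usually contradict each other.* Mixed significance ranges from about 20% to 70% with the assumed effect. In the benefit scenario with the most disagreement, it almost always means some significant and some not; opposite significant findings are very rare.
- *Women will move from drugs to alcohol.* Nothing in the documents suggests it; those figures are conditional on assuming it.
- *The plan's error rate is about 25%.* That counts separate tests at two visits, which is not the planned model.
- *PTSD and substance use are co-primary in the sense that both must succeed.* The documents call both primary and give no joint rule.
- *A single any-use endpoint is the obvious cheap repair.* The DAST cut and the recall period are undefined, and the power loss for a single-class effect is large.

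**Conclusion.** The concern holds. The documents do not identify the deciding substance-use test, and Subsections 2.7 and 2.10 conflict with Section 3 over the instrument. With the four AUDIT/DAST versions each tested at .05 at one visit, the chance of at least one false-positive substance-use result is about 13–15%, and 18.6% at the independence limit, against a stated .05. The 13–15% rests on assumed use rates and correlations, 81 per arm, no cohort effect, two-sided tests (sidedness is not stated) and each test holding its own level. Stronger common correlation lowers it to about 11%. Claims from either visit or from the TLFB raise it by an amount that the documents do not allow one to fix. The change should be made, and made before outcome data are examined.

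**What to change.** 1. Reconcile Subsections 2.7 and 2.10 with Section 3: state whether the TLFB is collected, at which visits, and what role it has.
2. Name the deciding test or tests at one visit, with one version per instrument. For example, take the AUDIT score and the DAST score at the 4-month follow-up, each as the MSC–TAU contrast from the mixed model of Section 3, with Holm control at .05 across the two. State the recall period of whatever is chosen.
3. State that a claim of benefit names the substance class in which it was shown, and that alcohol and drug results are always reported side by side.
4. Make the yes/no versions, the other visit and any remaining measures supportive, reported with estimates and intervals.

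A single any-use composite is an acceptable alternative only if the DAST yes/no cut and the recall period are defined and its power loss for a single-class effect is accepted.

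The cost is protocol wording, since the AUDIT and DAST are already collected; more would be needed only if the TLFB is kept and is not yet being administered. Some power goes to the Holm split, at most the amounts shown above for a simple comparison, and fewer results can be claimed.
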